6. DEFINITIONS OF THE ENDPOINT COMPONENTS

6.1 Antiplatelet therapy discontinuation

Antiplatelet discontinuation is defined as P2Y₁₂ inhibitors and/or aspirin withdrawal for >5 days at the time of surgical procedure without bridging therapy with antiplatelet agents in the first 3 months after PCI with low risk characteristics and 6 months after PCI with high risk characteristics or any any antiplatelet therapy discontinuation without bridging therapy at any time after PCI. A detailed description on the perioperative management of oral antiplatelet therapy will be obtained for both aspirin and P2Y₁₂ inhibitors (ticlopidine, clopidogrel, prasugrel, and ticagrelor). This includes the time delay from drug interruption to surgery as well as the time from surgery to reintroduction of therapy. The use of any bridging strategy will also be recorded. According to the SAS 2 Consensus Document, in selected patients at high risk for both bleeding and ischemic events, when withdrawal of oral antiplatelet therapy is required, bridging with cangrelor or with a short-acting intravenous glycoprotein IIb/IIIa inhibitor (GPI) (tirofiban or eptifibatide) can be considered.

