In selected cases, according to the SAS 2 recommendations, a bridging of antiplatelet therapy should be considered. A bridge therapy indicates a strategy of temporary transition with an intravenous antiplatelet agent in patients on oral antiplatelet therapy typically consisting of aspirin and a P2Y12 inhibitor. This strategy is usually reserved for patients deemed at high thrombotic risk (who thus cannot safely interrupt oral antiplatelet therapy) undergoing non-deferrable surgery at high risk of bleeding, which requires a predictable interruption of platelet inhibition at the time of the intervention [3-6].

The only intravenous antiplatelet agents available for clinical use, and thus of potential utility for antiplatelet bridging, include cangrelor and glycoprotein IIb/IIIa inhibitors (GPI). Cangrelor is an intravenous analog of adenosine triphosphate with a potent, selective and specific affinity for P2Y12 receptors [63]. Given that cangrelor is not renally cleared, there is no need for dose adjustment in patients with impaired renal function. Reversible binding to P2Y12 receptors of this agent along with its very short half-life (3-6 minutes) allows for resumption of platelet function within 60 minutes of infusion cessation [64]. Cangrelor was recently approved for the reduction of thrombotic cardiovascular events in patients with CAD undergoing PCI who have not received an oral P2Y12 inhibitor prior to the PCI [65]. Cangrelor has also been specifically tested against placebo as a bridging agent among thienopyridine-treated patients undergoing coronary artery bypass grafting surgery (CABG) in the Bridging Antiplatelet Therapy With Cangrelor in Patients Undergoing Cardiac Surgery (BRIDGE) trial [66]. In conclusion, in line with the BRIDGE trial approach, if intended as a bridging agent, cangrelor can be commenced any time between the next expected dose of the P2Y12 inhibitor and within 72 hours from P2Y12 inhibitor discontinuation, and stopped up to 1 hour before the start of surgery.

Alternatively, small molecule GPI's (eptifibatide or tirofiban) may be considered for bridging therapy [67]. Compared with cangrelor however, these agents have a slower offset of

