3.2 Secondary Objectives

- To assess ischemic and hemorrhagic events in relation to the application of the Consensus Document. Length of any antiplatelet discontinuation and delay in performing surgical procedures will also be evaluated.

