4.2 Primary endpoint

- Rate of discontinuation of P2Y12 inhibitors and/or aspirin (without bridging) in the first 3 months after PCI with low risk characteristics and 6 months after PCI with high risk characteristics or any antiplatelet therapy discontinuation without bridging therapy

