4.3 Secondary endpoints

Patients undergoing non cardiac surgery:

- The composite of death, myocardial infarction, probable/definite stent thrombosis according the Academic Research Consortium definition⁴⁴ and bleeding events of Bleeding Academic Research Consortium (BARC) grade ≥ 3 at 30 days
- The composite of death, myocardial infarction and probable/definite stent at 30 days
- The incidence of bleeding events of Bleeding Academic Research Consortium (BARC) grade ≥ 3 at 30 days
- The type and the length of discontinuation of any antiplatelet therapy in patients undergoing non cardiac surgery according to time from PCI to surgery
- Rate of non cardiac surgical procedures within 12 months from PCI divided into quartiles (0-3, 3-6, 6-9, 9-12 months)
- Delay in performing non cardiac surgical procedure

Patients undergoing cardiac surgery:

- The composite of death, myocardial infarction, probable/definite stent thrombosis according the Academic Research Consortium definition⁴⁴ and bleeding events of Bleeding Academic Research Consortium (BARC) grade ≥ 4 at 30 days
- The composite of death, myocardial infarction and probable/definite stent at 30 days
- The incidence of bleeding events of Bleeding Academic Research Consortium (BARC) grade ≥ 4 at 30 days
- The type and the length of discontinuation of any antiplatelet therapy in patients undergoing cardiac surgery according to time from PCI to surgery
- Rate of cardiac surgical procedures within 12 months from PCI divided into quartiles (0-3, 3-6, 6-9, 9-12 months)
- Delay in performing cardiac surgical procedure

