6.3 Stent thrombosis

Probable/definite stent thrombosis will be defined according the Academic Research Consortium definition⁴². With regard to the primary endpoint of the study, the adjudication will follow a hierarchical order with death first, MI second and stent thrombosis third, mostly in the case of recurrent ischemia without enzyme elevation.

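### The primary endpoint is not coherent as written: on its most direct reading the open-ended limb absorbs the 3- and 6-month limb, and section 6.3 ties a death/MI/stent thrombosis order to it

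*Combined protocol and SAP*

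**What the plan says.** Section 4.2 builds the primary endpoint from two limbs joined by *or*. I call them the windowed limb and the open limb. The windowed limb is unbridged stopping of a P2Y12 inhibitor, aspirin or both, within 3 months of a low-risk PCI or 6 months of a high-risk PCI. The sentence ends: "6 months after PCI with high risk characteristics or any antiplatelet therapy discontinuation without bridging therapy".

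Section 6.1 restates the definition with differences. Its windowed limb requires "withdrawal for >5 days at the time of surgical procedure without bridging therapy with antiplatelet agents"; section 4.2 has no duration and does not say what the bridging must consist of. Its open limb reads "any any antiplatelet therapy discontinuation without bridging therapy at any time after PCI", with no duration and no description of the bridging.

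Three other places bear on the meaning:
- Section 2: "A bridge therapy indicates a strategy of temporary transition with an intravenous antiplatelet agent in patients on oral antiplatelet therapy".
- Section 3.2: "Length of any antiplatelet discontinuation and delay in performing surgical procedures will also be evaluated".
- Section 4.3: "The type and the length of discontinuation of any antiplatelet therapy in patients undergoing non cardiac surgery", with a parallel item for cardiac surgery.

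The stent thrombosis section (numbered 6.3, like the MI section before it) states: "With regard to the primary endpoint of the study, the adjudication will follow a hierarchical order with death first, MI second", with stent thrombosis third. Those events appear only among the secondary endpoints of 4.3, for example "The composite of death, myocardial infarction and probable/definite stent at 30 days". Section 6.2 assigns all-cause mortality to the primary analysis and the cardiovascular/non-cardiovascular split to a secondary one.

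**The concern.** When two criteria are joined by *or*, each must be able to catch cases that the other misses. Here the open limb appears to catch everything. If so, the features that tie the endpoint to time from PCI and to PCI risk have no effect on the count. The endpoint then becomes any unbridged discontinuation at any time, in a registry that section 4.4.1 opens to patients at any interval from stenting.

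If that was not intended, the text does not say what was. Two analysts following the protocol could then obtain different primary results from the same data. The choice would be made in a non-randomised comparison in which thrombotic risk is itself assigned at the time of analysis (4.5.3), and with two interim analyses planned (7.1).

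The order in section 6.3 adds a second uncertainty, because it speaks of a primary endpoint made of clinical events that 4.2 does not contain.

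**Working it through.** The plan gives no event rates for this endpoint, so there is no figure to reproduce. The check is logical, supported by counting profiles. Profiles are unweighted combinations of characteristics; they are not patients or rates.

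**1. Containment.** Aspirin and P2Y12 inhibitors are antiplatelet agents. If the open limb means any agent, and bridging means the same in both limbs, every event in the windowed limb meets the open limb.

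**2. Grid for a patient on aspirin plus a P2Y12 inhibitor, unbridged.** Time from PCI (0-3, 3-6, >6 months) x PCI risk (low, high) x agent stopped (P2Y12 inhibitor, aspirin, both) x duration (≤5, >5 days) = 3 x 2 x 3 x 2 = 36. Three of the six time-by-risk cells are in the window (0-3 low, 0-3 high, 3-6 high). Under 6.1 the windowed limb alone counts 3 x 3 x 1 = 9.

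| Open limb read as | Open limb | Overlap | Either limb | Added by windowed limb |
|---|---|---|---|---|
| Any agent, no duration | 36 | 9 | 36 | 0 |
| Any agent, >5 days | 18 | 9 | 18 | 0 |
| All agents, no duration | 12 | 3 | 9 + 12 − 3 = 18 | 6 |
| All agents, >5 days | 6 | 3 | 9 + 6 − 3 = 12 | 6 |

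Under 4.2, with no duration, the windowed limb counts 3 x 3 x 2 = 18. Any agent gives 36 with 0 added. All agents gives 18 + 12 − 6 = 24 with 12 added.

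**3. Wider grid, adding single-drug patients and heparin.** There are 8 patterns of drugs taken and stopped (4 on both drugs, 2 on aspirin only, 2 on a P2Y12 inhibitor only). These are crossed with 5 durations (3, 5, 6, 7, 10 days), 3 bridging states (none, intravenous antiplatelet, low-molecular-weight heparin), 2 risks and 6 times (1, 2, 4, 5, 8, 14 months): 8 x 5 x 3 x 2 x 6 = 1,440. Windowed-limb events under 6.1: 5 stopping patterns x 3 durations over 5 days x 2 states without an intravenous antiplatelet x 6 in-window cells (2 low, 4 high) = 180.

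- Any agent, bridging as in section 2: 0 of 180 fall outside the open limb, and moving the window changes 0 of 1,440 profiles. Applying >5 days to both limbs gives the same result.
- All agents: 2 x 3 x 2 x 6 = 72 of 180 fall outside, and the window matters in 2 x 3 x 2 x 12 = 144 of 1,440. All 72 are patients on two drugs who stop one. For a patient on one drug, any and all coincide.
- Any agent, but heparin counts as bridging in the open limb only: 5 x 3 x 1 x 6 = 90 of 180 fall outside, and the window matters in 5 x 3 x 1 x 12 = 180 of 1,440.

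**4. Duration.** In 6.1 the >5-day criterion is in the windowed limb only. If it stays there and the open limb means any agent, it has no effect (36 either way). If it carries over, the count falls from 36 to 18. Section 2 describes P2Y12 wash-outs of 5 and 7 days. A 7-day stop passes a >5-day test and a 5-day stop does not, so the unresolved wording decides whether a 5-day unbridged stop is a primary event.

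**5. Clinical-event order.** Section 4.2 contains no death, MI or stent thrombosis, so an adjudication order for these events has nothing to act on in the primary endpoint. It fits the death, MI and stent thrombosis components of the composites in 4.3.

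**The case against.** The any-agent reading can be contested. The sentence changes from P2Y12 inhibitors and/or aspirin to antiplatelet therapy in general, which suggests a change of meaning, and a reading that empties half of a definition is usually disfavoured. Section 2 says most procedures can be done on aspirin, with P2Y12 wash-out where needed; any-agent counting would make each such unbridged wash-out a primary event however long after PCI. That points to total interruption. The usages in 3.2 and 4.3 are descriptive items, not event definitions. The open limb also omits the words specifying antiplatelet bridging, while 4.5.3 captures low-molecular-weight heparin and 6.1 records any bridging strategy. Finally, if any-agent is simply correct, the surplus words bias nothing.

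Much of this stands. Containment depends on the reading, and redundancy alone is harmless. But no sentence states total interruption or a wider meaning of bridging, and section 2 describes bridging as intravenous antiplatelet treatment. The objection therefore confirms the defect: the readings give different counts and the text does not choose.

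Stronger inferences are tempting but not supported:
- *Only about 5-10% of patients are in the window.* 0.20 x 1623 = 324.6; spread evenly over a year, 3/12 gives 81 and 6/12 gives 162. But 7.1 attaches the 20% to group 1, and no distribution of time from PCI is given.
- *The wording favours one group.* No discontinuation or bridging frequencies are given by group, so no direction follows.
- *Section 6.3 sets up a rival primary endpoint.* It gives only an adjudication order. Section 6.2 may likewise mean just the main analysis of death.
- *The risk strata are undefined.* The Consensus Document is an appendix (section 5) that was not available for this review, so nothing is claimed.

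**Conclusion.** The point holds as incoherent wording of the primary endpoint, to be corrected before groups are compared. On the most direct reading the windows and risk strata change no primary count. That conclusion rests on two assumptions: the open limb means any agent, and bridging means an intravenous antiplatelet agent in both limbs. If either fails, the windows matter. A reader should not conclude that they are inert on every reading.

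No magnitude or direction is claimed. The any/all distinction affects only patients on two or more agents, a share the documents do not give, and the profile counts show only that the readings differ.

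Two further findings do not depend on the reading: the >5-day criterion is in 6.1 but not in 4.2, and the reference to the primary endpoint in the stent thrombosis section conflicts with 4.2.

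**What to change.** Before any comparative analysis, including the interim at 800 patients:

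1. Put one identical primary definition in 4.2 and 6.1. If a two-limb composite is intended, word it so that neither limb contains the other, for instance by stating that the open limb means all antiplatelet agents stopped, if that was the intent. If any unbridged discontinuation at any time is intended, remove the windows and strata from the primary definition and report them as a subgroup breakdown.
2. Use the same bridging wording in both limbs.
3. Reconcile the duration criterion between 4.2 and 6.1 and state which limb or limbs it applies to. No value is proposed here.
4. In the stent thrombosis section, refer to the death, MI and stent thrombosis components of the 4.3 composites instead of the primary endpoint, and clarify the primary-analysis label in 6.2.
5. Recheck the sample-size basis in 7.1 against the chosen definition.

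The cost is a wording amendment and possibly fewer countable events. No new data are needed: stop and restart dates (4.5.3) and bridging use (6.1) are already recorded. The change affects how events are counted, not how patients are managed.

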Cardiologists defined the thrombotic risk based on a series of clinical features and procedural characteristics. In particular, the definition of thrombotic risk (low, intermediate or high) was derived after careful revision of the literature which led to the formulation of a tables which summarized the information obtained. All Cardiology members of the Writing Committee provided their feedback until a consensus was reached. Surgeons classified all interventions according to the inherent hemorrhagic risk (low, intermediate, or high) of each specific surgery. In particular, bleeding risk was not solely based on the amount of blood loss, but mostly according to the anticipated difficulty in achieving adequate local hemostasis. The bleeding risk was defined in a total of about 250 surgical procedures. Finally, the most appropriate antithrombotic treatment regimen in the perioperative phase was defined for each procedure taking into consideration both the thrombotic and bleeding risk profiles. Ultimately, a consensus agreement was reached which involved not only cardiologists and surgeons, but also anesthesiologists and hematologists. Importantly, the recommended antithrombotic treatment regimen was not standard to a given thrombotic/bleeding risk profile, but was specific to each individual surgical specialty.

In general, if surgery cannot be delayed, it should be performed after the first month and ideally after at least 3 months from PCI [25, 32, 46, 49]. The vast majority of procedures may be performed while on aspirin, with the possible exception of surgeries at extremely high risk of bleeding (e.g., neurosurgery). When a wash-out of P2Y12 inhibiting therapy is required, this should be performed judiciously according to the timing of surgery: 5 days for clopidogrel and ticagrelor and 7 days for prasugrel. Recent data from a large observational study in CABG patients demonstrated that discontinuation 3 days before surgery, as opposed to 5 days, did not increase the incidence of major bleeding complications with ticagrelor (OR 0.93 (95% CI 0.53-1.64), p=0.80), but increased the risk with clopidogrel (OR 1.71 (95% CI 1.04 – 2.79), p=0.033 [71]. On the basis of these findings, in selected cases, surgery might be performed after 3 days of

ticagrelor discontinuation.

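### As literally worded, the second limb of the primary endpoint scores unbridged stops that the SAS 2 summary allows the same as stops it advises against, and makes the first limb's limits redundant

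*Combined protocol and SAP*

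**What the plan says.** The primary endpoint has two limbs joined by 'or'.

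- **First limb.** Section 6.1 covers both drug types, P2Y12 inhibitors and aspirin, and counts "withdrawal for >5 days at the time of surgical procedure without bridging therapy with antiplatelet agents in the first 3 months after PCI". That window is for PCI judged low risk; for high-risk PCI it is 6 months. Section 4.2 has the same windows but no day cut-off.
- **Second limb.** Section 4.2 adds "or any antiplatelet therapy discontinuation without bridging therapy". Section 6.1 leaves this limb open in time as well, and counts "any antiplatelet therapy discontinuation without bridging therapy at any time after PCI". Neither section limits it by duration, drug, risk class or operation.

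The protocol's own account of the Consensus Document covers the same decisions:

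- **Wash-out.** Section 2 says "When a wash-out of P2Y12 inhibiting therapy is required, this should be performed judiciously according to the timing of surgery", and gives 5 days for clopidogrel and ticagrelor and 7 days for prasugrel. It also allows that aspirin may be an exception in surgery at extremely high bleeding risk.
- **Bridging.** Section 2 says "This strategy is usually reserved for patients deemed at high thrombotic risk" who are having non-deferrable surgery at high bleeding risk. Section 6.1 says it can be considered "in selected patients at high risk for both bleeding and ischemic events, when withdrawal of oral antiplatelet therapy is required".

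Section 4.5.3 derives each patient's thrombotic and hemorrhagic risk under the Document at analysis. The endpoint does not use either one.

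**The concern.** A patient outside the selected high-risk group who needs a wash-out will, on the protocol's summary, stop the drug without bridging. The second limb scores that stop as a primary event, exactly as it scores a stop that the Document advises against.

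The groups are defined by use of the Document (sections 4.1 and 7.1), and the primary objective is to assess outcomes associated with applying it (section 3.1). If the event count mixes stops made under the Document with stops made against it, a difference between the groups has no clear meaning. A low rate could reflect good adherence, reluctance to stop any drug, or bridging well beyond the selected patients. Section 7.2 sharpens this: patients at Document centres who were not managed with it are excluded, so the events left in group 1 would largely be stops made under the Document.

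**Working it through.** **1. The plan's own figure.** Section 7.1 gives 1,623 patients, 80% power, 5% significance and 1:2 matching, with 324 vs 162 within one year of stenting. It states no event rates or effect size, so neither 1,623 nor 486 (= 324 + 162) can be re-derived. The only link found is 0.20 × 1,623 = 324.6. The check is therefore one of logic, followed by illustrations on assumed rates.

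**2. Redundancy.** Every event under the first limb is an unbridged stop after PCI. If the second limb covers any single drug for any length of time, it already contains every first-limb event. The >5-day, 3-month and 6-month limits then exclude nothing.

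**3. Care patterns scored under the literal endpoint.**

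| Care pattern | Against the SAS 2 summary | Primary event? |
|---|---|---|
| Wash-out, unbridged, outside the selected high-risk group | allowed | yes |
| Unbridged stop where the Document advises against it | departure | yes |
| Wash-out with bridging, selected high-risk patient | allowed | no |
| Nothing stopped, although the Document foresees a stop | departure | no |
| Every stop bridged, beyond the selected patients | departure | no |

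Allowed care and departures appear on both sides of the count.

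**4. The narrower reading.** Suppose the second limb means stopping all antiplatelet therapy. A P2Y12 wash-out on continued aspirin outside the window is then not an event. Inside the window the first limb still applies: 5 days is not >5, but 7 days is. An unbridged 7-day wash-out therefore still scores.

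**5. Possible dilution (all inputs assumed).** Splitting 1,623 in the ratio 1:2 gives 541 (group 1) and 1,082 (group 2). The protocol does not state this split. Let non-concordant stops be 5% vs 10%, and add the same share of allowed unbridged stops to both groups. Power = Φ[(|p1 − p2| − 1.96·s0)/s1], with s0 = √[p̄(1 − p̄)(1/n1 + 1/n2)] and s1 = √[p1(1 − p1)/n1 + p2(1 − p2)/n2].

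| Added allowed stops | Rates compared | s0 | s1 | Power |
|---|---|---|---|---|
| none | 5% vs 10% | 0.0146 | 0.0131 | 0.95 |
| 10 points | 15% vs 20% | 0.0204 | 0.0196 | 0.70 |
| 20 points | 25% vs 30% | 0.0237 | 0.0233 | 0.56 |
| 40 points | 45% vs 50% | 0.0263 | 0.0262 | 0.48 |

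**6. Possible reversal (all inputs assumed).** Let s be the share of patients in whom the Document supports an unbridged stop. A fully concordant centre scores s. Let a local-practice centre stop only half of those patients, and wrongly stop 10% of the rest. It scores 0.5s + 0.1(1 − s) = 0.1 + 0.4s.

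- s = 10%: 10% (Document) vs 14% (local).
- s = 30%: 30% vs 22%. The Document centre looks worse, although departures in both directions are 0% vs 0.5 × 30% + 0.1 × 70% = 22%.
- The two rates are equal at s = 0.1 + 0.4s, so s = 1/6, about 17%.

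The direction depends on s, and the documents do not give s.

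**The case against.** The strongest reply is that the literal reading cannot be intended, because it empties the first limb. Stopping all antiplatelet therapy without bridging is a reading that gives both limbs content. Section 2 says most procedures can be done on aspirin, so allowed stops would then seldom count through the second limb. Section 2 also prefers surgery at least 3 months after PCI, which limits allowed stops inside the window. This stands as a reason for caution: the overlap may be small. It does not remove the point, because the text does not state that reading and step 4 leaves an overlap even under it.

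Three further replies have weight.

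- The full Consensus Document, which section 5 says is enclosed, was not in the text available for this review. How often it supports an unbridged stop is unknown.
- Application of the Document is the exposure, not the endpoint. It would be wrong to say that the endpoint must itself measure adherence.
- Some material is already planned. Section 4.3 reports type and length of discontinuation by time from PCI, and has 30-day ischemic and bleeding endpoints. Section 6.1 records aspirin and P2Y12 inhibitors separately. None of this labels a stop as agreeing with the Document or not.

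A reader might infer that a centre which never stops a drug scores best. It only ties at zero with a centre that bridges every stop. A reader might also infer that group 1 will look worse for following its own guidance. That needs local centres to stop less often than the Document allows, and the documents give no evidence of it.

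**Conclusion.** The point holds as a defect of definition. On the literal wording, the second limb makes the first limb's limits redundant and puts allowed and non-allowed unbridged stops in one category. On the narrower wording the overlap shrinks, mainly to the 7-day wash-out inside the window. On either wording, never stopping and bridging everything both score zero, so the primary rate alone cannot separate following the Document from departing from it.

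Dilution and reversal are possible, not shown. The power figures (0.95 falling to 0.70, 0.56 and 0.48) and the reversal example rest wholly on assumed rates, and the 541 vs 1,082 split is also an assumption. The documents do not support a claim that the primary result will be biased in a given direction or by a given amount. The point matters because it limits what the primary comparison can conclude, and it can be repaired with data already planned for collection.

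**What to change.** 1. Reconcile sections 2, 4.2 and 6.1. State which stops the second limb counts, any single drug or all antiplatelet therapy, and how it relates to the first limb's duration and window limits.
2. Keep the primary rate. In both groups, report it split into stops concordant and non-concordant with the Document, with aspirin and P2Y12 inhibitors shown apart.
3. Classify by one fixed rule, written before analysis and applied identically to both groups. It should use the Document's recommendation for the patient's risk classes (section 4.5.3) and for the specific procedure and specialty, with the recorded stop, restart and bridging data. Risk classes alone are not enough, because section 2 says the recommended regimen is specific to each surgical specialty.
4. Also count departures in the other direction: drug continued, or bridged, where the Document foresees an unbridged stop. Counting only non-concordant unbridged stops would still give zero to a centre that never stops a drug.

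**Cost.** Wording changes in sections 4.2 and 6.1, and a procedure-level derivation rule to program; section 2 mentions about 250 classified procedures. The planned data items should suffice.

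**Limit.** The exclusion in section 7.2 partly builds low non-concordance into group 1, so the split should be read alongside the 30-day ischemic and bleeding endpoints. No clinical rule is proposed here; which stops and which bridging are appropriate is for the authors to settle.
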